University International Centre for point-of-care testing, St. Vincent's Hospital, and the Australasian Society for HIV, Viral Hepatitis and Sexual Health Medicine (ASHM). Flexible training resources will be developed specifically for operator use in the required clinical settings. The training program will be delivered to operators using well established training pathways via remote learning platforms, such as GoToMeeting, website tutorials, and other online resources. The training will include pre-analytical (e.g. specimen collection, cartridge preparation, analytical (e.g. test operation including use of software and middleware) and post-analytical components (results interpretation and recording, waste disposal, and environmental decontamination) required to accurately perform patient tests. The HCV point-of-care testing program will also implement a quality system, consistent with best practice and regulatory standards and based upon successful existing programs currently in place for infectious disease pointof-care testing. This program provides an excellent opportunity to prospectively evaluate the effectiveness of the operator training with regard to knowledge improvement, practical competency and professional conduct for performing point-of-care and dried blood spot testing for HCV infection. This data will be useful in the assessment of training effectiveness across different trainee occupations and will be utilised to improve training processes for scale-up of point-of-care and dried blood spot testing. **Study Objectives** This study aims to address several objectives among people participating in point-of-care and dried blood spot testing for HCV infection clinical education, operator training, external quality assurance, and internal quality control programs, including: 1) To evaluate changes in self-reported knowledge about point-of-care and dried blood spot testing for HCV infection; 2) To evaluate changes in self-reported competency in performing point-of-care and dried blood spot testing for HCV infection; 3) To evaluate the concordance of quality control and external quality assurance testing with the expected results in the program; 4) To evaluate the proportion of operators who participate and complete the quality control and external quality assurance program; 5) To evaluate the proportion of tests with error or invalid results; 6) To evaluate the proportion of error/invalid test with a successful repeat point-of-care test. This study will be conducted at services (either needle and syringe programs Study Setting or health services) in Australia. It is envisaged that each site will consent and train a maximum of 4 participants for participation in an operator training, quality assurance, and quality control programs for point-of-care and dried blood spot testing for HCV infection. **Participant** Depending on the exact number of operators undertaking and completing population training at each site, it is anticipated that 100-150 operators will be enrolled and will participate in an operator training, quality assurance, and quality control program for point-of-care and dried blood spot testing for HCV infection. Participants/operators will consist of nurses, physicians, needle and syringe program staff, peer-support workers, other health workers and other staff who have an interest to be appropriately trained. Eligibility criteria Operators at the service are eligible for inclusion if the following criteria are met: 1) Provide written informed consent 2) >18 years of age 3) Staff member who will be performing point-of-care or dried blood spot testing for HCV infection.

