At enrolment, participants will complete a self-administered, online survey. The survey will collect information on demographic characteristics (age, gender), the type of service at which participants are employed, role in service, personal experience with HCV testing and treatment for HCV (e.g. numbers tested and treated), knowledge of hepatitis C infection, and knowledge of HCV point-of-care testing and dried-blood-spot testing. A 5-point Likert scale will be utilised to measure participants' HCV-related competence in (i) ensuring people at risk for HCV are regularly screened, (ii) interpreting test results and diagnose HCV, (iii) collection of a fingerstick sample, (iv) performing dried blood spot HCV testing, (v) performing point-of-care HCV testing, (vi) operating the GeneXpert machine. Participants graded own competence in the six five categories by selecting either (1) Not at all confident, (2) Slight knowledge, skills or competence, (3) Average

competence amongst peers, (4) Confident and competent, (5) Very confident and competent.

All participants will complete a self-administered, online survey following each stage of the operator training process, including completion of the: online pre-requisite learning modules, theoretical operator training, practical operator training and at 6 months post-training completion; and quality assurance/quality control.

Study Procedures

Study Visit	Screening (Enrolment)	Pre- requisite Learning	Theoretical Training	Practical Training	6-month Post- training Review
Informed consent	Х				
Survey (Screening version)	х				
Survey (Follow-up version)		Х	Х	Х	Х

To evaluate the quality system participation rate and the concordance of quality control and external quality assurance testing with the expected results in the program, data will be collected at defined intervals from the GeneXpert devices, evaluated for concordance with the expected result and recorded on a quality control or quality assurance spreadsheet.

We will use data from the point-of-care connectivity systems to measure the uptake of point-of-care testing, error rates (proportion of point-of-care tests with an error code), invalid rates (proportion of point-of-care tests with an invalid result) and successful re-tests (proportion of errors/invalid, with a successful repeat point-of-care test). These data will be provided back to operators as part of the process for improved performance in a summary feedback report.

Study analysis

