The population attending HCV education and training sessions will be characterised using descriptive analyses. The frequency and proportion of each participant who responded to surveys at each stage of the operator training process, including online pre-requisite learning modules, theoretical operator training, practical operator training; and quality assurance/quality control will also be evaluated.

We will evaluate knowledge and self-perceived competency related to HCV management and treatment. Competency scores will be re-categorised into a binomial 0/1 response, where 0 indicates little or no competency and includes: (1) Not at all confident, (2) slight knowledge, skills, or confidence, and (3) Average competence amongst peers, and 1 indicates confidence and competence including responses: (4) Confident and competent, and (5) Very confident and competent. Using a McNemar's test for binomial paired data, we will test for a significant change in competency (from baseline (pretraining) to follow-up (6 months post-training) and significance of this change for self-reported participant ability in (i) ensuring people at risk for HCV are regularly screened, (ii) interpreting test results and diagnose HCV, (iii) collection of a finger-stick sample, (iv) performing dried blood spot HCV

testing, (v) performing point-of-care HCV testing, (vi) operating the GeneXpert device among participants who answered all four surveys. Factors associated with poor self-perceived (little/no competency) will be assessed using logistic regression analyses.

We will also assess if knowledge or self-perceived competence leads to improved practice (e.g. lower proportion with error or invalid test results).

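### The operator-training appendix names McNemar's test and logistic regression without accounting for site, so p-values for change and for site-level factors are too small if operators at a site resemble one another

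*Protocol*

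**What the plan says.** Appendix 26.1 describes an observational study of the staff who learn to run the two tests. Under Study Setting, "each site will consent and train a maximum of 4 participants for participation"; under Participant population, "it is anticipated that 100-150 operators will be enrolled and will participate".

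The Study analysis entry fixes two inferential methods:

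- **Change from before training to six months after it, on six competency items:** "Using a McNemar's test for binomial paired data, we will test for a significant change in competency".
- **Predictors of low competency:** "Factors associated with poor self-perceived (little/no competency) will be assessed using logistic regression analyses".

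The enrolment survey (Study design entry) records, among other characteristics, "the type of service at which participants are employed, role in service", along with age, gender and experience of HCV testing and treatment. The appendix does not say which of these will be used as factors.

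Site does not appear in either analysis. By contrast, Section 14.5 clusters the main trial's comparison on site, using GEE with robust standard errors.

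**The concern.** McNemar's test assumes that the pairs, here the operators, are independent of one another. Logistic regression with model-based standard errors makes the same assumption. The appendix itself describes a structure in which several operators belong to one site. If they tend to rate themselves alike, or to gain or lose confidence together, each additional operator at a site brings less than one operator's worth of information.

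The cost would be false positives of two kinds: a change in competency declared on too little evidence, and a characteristic of the service declared a predictor of low competency when it is not. The appendix says the results are meant to improve the training as testing is scaled up, so a spurious site-level association could misdirect that effort.

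**Working it through.** **Inputs**

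- Operators per site: at most 4 (Appendix 26.1, Study Setting).
- Operators in total: 100 to 150 (Participant population). At 4 per site this needs at least 100/4 = 25 to 150/4 = 37.5, so 38, sites.
- Significance level: not stated for this study; 5% two-sided is assumed.
- Intracluster correlation (ICC): not stated for operators; 0.05 to 0.20 is assumed. The 0.05 in Section 14.3 is for treatment initiation among trial participants and is not evidence about operators.

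The appendix gives no sample-size or power figure for this study, so there is nothing of its own to reproduce.

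**Formulas**

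Design effect DE = 1 + (m − 1) × ICC, with m operators per site. The true error of a nominal 5% test that ignores site is 2 × [1 − Φ(1.96/√DE)]. This applies to a factor constant within site, with the ICC of the outcome, and to McNemar's test, with the ICC of the change.

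| m | ICC | DE | 1.96/√DE | True error |
|---|---|---|---|---|
| 4 | 0.05 | 1.15 | 1.828 | 6.8% |
| 4 | 0.10 | 1.30 | 1.719 | 8.6% |
| 4 | 0.20 | 1.60 | 1.549 | 12.1% |
| 2 | 0.05 | 1.05 | 1.913 | 5.6% |
| 2 | 0.10 | 1.10 | 1.869 | 6.2% |
| 2 | 0.20 | 1.20 | 1.789 | 7.4% |

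For these two kinds of analysis at m = 4 and ICC 0.10, 100 operators carry the information of 100/1.30 ≈ 77 independent ones, and 150 that of 150/1.30 ≈ 115.

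**Check by simulation, McNemar** (4 operators per site, 20,000 runs per setting, no true change, 40% discordant pairs assumed)

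| ICC of the change | 25 sites | 38 sites | Formula |
|---|---|---|---|
| 0 | 5.0% | 5.1% | 5.0% |
| 0.04 | 6.5% | 6.4% | 6.4% |
| 0.08 | 7.7% | 7.8% | 7.8% |
| 0.16 | 10.6% | 10.9% | 10.7% |
| 0.24 | 12.9% | 13.5% | 13.5% |

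**Check by simulation, logistic Wald test of a binary factor with no true effect** (38 sites of 4, 20,000 runs per setting, 30% prevalence assumed)

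| ICC of the outcome | Factor constant within site | Operator-level factor unrelated to site | Factor balanced within site |
|---|---|---|---|
| 0 | 4.9% | 4.7% | 4.5% |
| 0.06 | 7.3% | 4.5% | 4.5% |
| 0.12 | 9.0% | 5.1% | 4.0% |
| 0.21 | 12.4% | 4.9% | 2.5% |

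The formula and the simulations agree. The last table also shows that the direction of the error depends on the level at which the factor varies. It is inflated for a site-level factor, absent for a factor unrelated to site, and reversed for one balanced within site.

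**The case against.** The case against giving this much weight is substantial, and most of it stands.

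- **Not every p-value is affected.** A reader might infer that all the logistic p-values are too small. They are not. Among the characteristics collected, only type of service is plainly common to a whole site. Role, age, gender and experience vary between colleagues, and for these the unadjusted test is about right or conservative.
- **McNemar's test compares each operator with himself or herself.** A stable site effect on competency largely cancels; only correlation of the change within site matters. Training is delivered remotely, the surveys are self-administered online and competency is observed individually, so that correlation may be small.
- **No operator ICC is documented.** A reader might carry over the 0.05 from Section 14.3 as the trial's own figure for this purpose. It describes a different outcome in different people.
- **Four is a ceiling.** Many sites may train fewer. Restricting the change analysis to those who answered all four surveys can only make the clusters smaller.
- **Some of this could be settled in an analysis plan.** For the logistic regression that is fair, since site-robust errors would not contradict the text. For the change analysis it is weaker, because the appendix names a specific test whose standard form assumes independent pairs.
- **The contrast with Section 14.5 has limits.** The main trial randomises sites and this study does not. The contrast shows that site is recognised elsewhere in the Protocol, not that the same adjustment was owed here.

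What remains is that the appendix describes operators nested in sites and then names analyses that take no account of it.

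**Conclusion.** The point holds as a conditional and modest one. If change in competency is positively correlated within site, the McNemar p-values are too small. If competency itself is, so are the logistic p-values for factors constant within site. At four operators per site, a nominal 5% becomes about 7%, 9% or 12% at an assumed ICC of 0.05, 0.10 or 0.20, where for McNemar the ICC is that of the change. At two per site the corresponding figures are 5.6%, 6.2% and 7.4%. The inflation is slight at the low end and becomes clear only from an ICC of about 0.1 to 0.2.

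These sizes rest on assumed ICCs, a 5% level and sites of equal size. The simulations also assume 40% discordant pairs and 30% prevalence.

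A reader might take this as a flaw in the trial's results. The documents do not support that: the issue is confined to an observational appendix study, and the primary comparison in Section 14.5 already clusters on site. It is a worthwhile improvement because it is cheap, not because a conclusion of the trial depends on it.

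**What to change.** In the Study analysis entry of Appendix 26.1, state that:

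1. The change from baseline to six months is tested with a cluster-adjusted McNemar test, or with a logistic GEE that has survey time as covariate and site as the cluster. Clustering at site level also covers the two responses from the same operator.
2. Factors associated with low competency are assessed by logistic GEE with site as cluster, or by logistic regression with site-robust standard errors. Either should carry a small-sample correction, because about 25 to 38 sites is few for an uncorrected robust variance.

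The later comparison of competency with error and invalid rates names no method. Accounting for site there too would be sensible, but is only a recommendation.

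**Cost:** one or two sentences and a cluster option in the software. The only added data requirement is that each operator's record carries a site identifier. Intervals for change and for site-level factors will be somewhat wider where correlation exists; for factors that vary within site they may stay the same or narrow.
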